## 12.6 Exclusion Criteria:

| Order Number      | Criteria  |
|-------------------|---|
| Subject Exclusion |   |
| 1                 | 
1. Age < 18 years old or > 89 years old
 2. Currently presenting with psychosis as determined by mental health consultant
 3. Have a history of Cognitive disorder that would impair understanding of consent
 4. Have a personal/family history of Schizophrenia
 5. Currently pregnant or nursing
 6. Serious and unstable medical condition/problems
 7. Inability to medically clear
 8. Non-English Speakers
 9. Civilian Humanitarians
 10. Have previously enrolled in this study
 |

## 13.0 Recruitment and Consent

### 13.1 Please describe the recruitment process, including how subjects will be identified and selected for the study.

#### Subject Recruiting Methods

The method for subject recruitment is demonstrated in Figure 1. Explicitly they are as follows:

1. Patient Identification/Pre-screening
  1. Clinician will subjectively identify patients who present to the ED that express SI
  2. Clinician or nurse reviews EMR for documented inclusion/exclusion criteria
  3. Clinician will medically clear patient
2. Screening: The mental health liaison interviews patient, and along with the on-call mental health provider, determines whether or not patient requires inpatient psychiatric hospitalization.

3. Screen positive: Eligible patients, who are being hospitalized on inpatient psychiatry, are approached for consent. If intoxicated on presentation, they are approached when clinically sober.
4. Consent is obtained:
  1. Patient will complete BSSI & MADRS-S
  2. Treatment is administered per protocol
  3. Vitals and ADR are monitored
5. Potential medication contraindications will be identified by treating physician, and a pharmacy consult will be obtained at the physician's discretion

### 13.2 Compensation for Participation:

Subjects enrolled in the study will not be compensated monetarily.

### 13.3 Please describe the pre-screening process. If no pre-screening, enter Not Applicable in the text editor

All procedures in the management of the acutely suicidal patient will be in accordance with the standard of care, which includes a focused history and physical by an Emergency Medicine physician. Figure 1 demonstrates the flow of investigational procedures. The EM provider shall medically screen the patient and include appropriate ancillary studies. For example, if a patient is altered, intoxicated, sick-appearing, or exhibiting a clinical toxicodrome, standard labs, EKG, or imaging will be ordered per standard of care. All female patients will have a urine HCG documented. Then, screening for admission to the psychiatric department will be done by the mental health liaison. This standard procedure will serve secondarily as the pre-screening method for this investigation. This will minimize duplication of work.

### 13.4 Consent Process: Revised Common Rule, Section 219.116: General requirements for informed consent, whether written or oral, are set forth in this paragraph and apply to consent obtained in accordance with the requirements set forth in paragraphs (b) through (d) of this section. Broad consent may be obtained in lieu of informed consent obtained in accordance with paragraphs (b) and (c) of this section only with respect to the storage, maintenance, and secondary research uses of identifiable private information and identifiable biospecimens.

Are you requesting a waiver or alteration of informed consent?

Yes  No

Please explain the consent process:

#### Informed Consent Procedures

Research team members will review study procedures, potential risks and benefits of the study. Informed consent procedures will be conducted in private offices or exam rooms located in the ED. In accordance to 32 CFR 219, under no circumstances will the supervisors or commanding officers to the potential subject allowed to be present during the consent process. This is to ensure the avoidance of undue influence or coercion that may stem from the nature of the superior-subordinate relationship.

The patient will be approached for informed consent in accordance to with 21 CFR 50. They will be provided with a written document that embodies the elements of the informed consent. The consent will be presented orally to the subject with a witness. Once presented the subject will be given a reasonable time to review the contents and inquire information. All questions will be answered by the investigator obtaining consent. If consent is granted, the subject and the investigator will sign the consent form. A copy of the informed consent document will be given to the subject, and the original will be retained by the study investigator. This consent form will not be tied to any medical or data records. Consent forms will be maintained in a research specific locked drawer located in an investigator's/coordinator's office and only accessible by study the primary investigator, associate investigators or coordinator. The locked consent will be checked by the P.I. or A.I. weekly.

In accordance with North Carolina State Law, if subjects are unable to consent for themselves due to emergent situations or impaired status, a LAR will be approached for consent. In the context of this study, subjects in these circumstances will be excluded from recruitment. If they are clinically intoxicated, consent will not be sought until they are clinically sober. Decisionally impaired subjects will not be approached for consent.

## Vulnerable Populations

Due to the fact investigations take place in the ED, vulnerable populations that will be recruited are persons in an emergency situation presenting with situational cognitive vulnerabilities. Protections for this process have been put in place during the selection, and informed consent process. Furthermore, the selection of an interdepartmental research monitor will ensure the utmost care of this vulnerable population.

Under the Common Rule, DoDI 3216.02 military members are not considered a vulnerable population. However, due to the nature of hierarchical social structure they are more susceptible than the general population. Protections for this population will be in place during the consent process, and have been added to the consent verbiage.

### **13.5 DoDI 3216.02 requires an ombudsman to be present during recruitment briefings when research involves greater than minimal risk and recruitment of Service members occurs in a group setting. If applicable, you may nominate an individual to serve as the ombudsman.**

N/A  
 Propose ombudsman

### **13.6 Withdrawal from Study Participation:**

Explain the process for withdrawal and specify whether or not the subjects will be given the opportunity to withdraw their data or specimens in the event they wish to withdraw from the study

Per Informed Consent Form:

"If you choose to participate, you are free to ask questions or withdraw from the project at any time without prejudice to your future care. Any new significant findings developed during the course of the research, which may affect your willingness to participate further, will be explained to you. Please notify [name] at [contact], [name] at [[contact]](mailto:[contact]) or [name] at [contact] to ensure an orderly termination process.

If you withdraw, you will no longer receive study drugs or treatments that are part of the study, unless these are also part of your normal drugs or treatments. Your withdrawal will involve no loss of benefits to which you are otherwise entitled. If you withdraw from this study, your data will be included in the data analysis for this project."

## **14.0 Risks and Benefits**

### **14.1 Risks of Harm:**

Identify all research-related risks of harm to which the subject will be exposed for each research procedure or intervention as a result of participation in this study. Consider the risks of breach of confidentiality, psychological, legal, social, and economic risks as well as physical risks. Do not describe risks from standard care procedures; only describe risks from procedures done for research purposes

#### **List and Document Risks**

The overall risk of an adverse event while using ketamine is very low, and easily manageable. Low dose IV ketamine can cause:

1. Transient Psychedelic effects – disturbances in visual and auditory perception, mood, body image, and time.
2. Hemodynamic changes – increase in blood pressure and heart rate

3. Psychotomimetic effects – mimicking the symptoms of psychosis, including delusions and delirium
4. Narcosis
5. Hypersalivation
6. Nausea and vomiting
7. Anxiety and Paranoia
  - o Respiratory depression, apnea, laryngospasm, hypotension, bradycardia, myocardial infarction, central diabetes insipidus, anaphylaxis, increased intraocular pressure, increased intracranial pressure, porphyria and death.

## (2) Justification of Risks

Ketamine holds a high degree of safety. In a review that describes over 70,000 patients only a single cardiorespiratory event of lasting significance was reported. Fully dissociative patients maintain their pharyngeal reflexes.

| Risk   | Justification & Mitigation  |
|--|---|
| 
Transient Psychedelic effects are disturbances in visual and auditory perception, mood, body image, and time. Patient may experience feelings of floating, conscious dreams, or hallucinations. These effects occur between 50 and 200 ng/ml with more severe effects at higher doses.
 | 
Dissociative symptoms are transient and will peak at 40 minutes and resolve within 120 minutes.
 
To mitigate psychiatric discomfort, pre-induction coaching will be provided. This is where the patient will be informed that they may have vivid dreams.
                       |
| 
Hemodynamic changes are extremely rare with ketamine use, especially with such a slow infusion.
  | 
Signs of psychiatric discomfort will be managed with titratable sedatives (eg, midazolam) on an as needed basis.
 
Will be monitored hourly. Mild increases in heart rate can be mitigated by sympatholytic agents.
   |
| 
Psychotomimetic effects
   | 
Treatment will be stopped if pulse or systolic blood pressure increases > 25% of baseline, respiratory rate is sustained at < 7, or if severe psychomimetic effects or agitation present.
 
Can be mitigated through slow infusion or concomitant use of benzodiazepines if needed clinically.
 |
| 
Narcosis (absence of verbal response) at 0.5 mg/kg. This phenomenon is more likely with a quicker infusion.
   | 
This will be lessened or negated by mixing the dosage of medication in 100cc of NS and infusing slowly over 40 minutes.
  |
| 
Hypersalivation. Less likely at this concentration and with slow infusion.
   | 
This side effect can be addressed with concomitant use of glycopyrrolate if clinically indicated.
   |
| 
Nausea and vomiting. Less likely at this concentration and with slow infusion. Generally, occur after emergence from dissociative state.
  | 
This side effect can be addressed with use of ondansetron if clinically indicated.
  |
| 
Psychopathological symptoms such as difficulties in abstract thinking, lack of spontaneity, and decrease flow of conversation. This phenomenon is more likely with a quicker infusion.
  | 
This will be lessened or negated by mixing the dosage of medication in 100cc of Normal Saline and infusing slowly over 40 minutes.
   |
| 
Anxiety and Paranoia can present at 500 ng/ml. This phenomenon is more likely with a quicker infusion.
  | 
This side effect can be addressed with use of a benzodiazepine if clinically indicated.
  |

**Acute Delirium** can present at high doses or too fast administration of low doses (5 to 10 mg).

**Transient respiratory depression** & Apnea. Extremely Rare occurrence may occur with rapid delivery or concomitant use of midazolam.  
Other **extremely rare**, serious adverse events have been reported:

- laryngospasm, hypotension, bradycardia, myocardial infarction, and death.

This will be mitigated by the low dosage used in this investigation coupled with the slower infusion rate of 40 minutes and can be treated with a benzodiazepine if clinically indicated.

This will be mitigated through appropriate weight-based dosing, slow infusion, careful monitoring of those on concomitant midazolam.  
Mitigation of these events will be through continuous hemodynamic monitoring including pulse oximetry.

- For full list of possible adverse drug reactions see Patient Drug Handout in Appendix D.

#### 14.2

#### Measures to Minimize Risks of Harm (Precautions, safeguards):

For each research procedure or intervention, describe all measures to minimize and/or eliminate risk of harms to subjects and study personnel

##### Minimization of Risks

In general, slow infusion of low-dose ketamine has been shown to significantly reduce reporting of moderate to greater side effects, specifically hallucinations and feelings of unreality. We will be excluding those patients most vulnerable to adverse events, such as those with a history of psychosis, schizophrenia, or schizoaffective disorder. Because Ketamine is pregnancy category B, they will be excluded from the study. Patients will also be excluded medically at the discretion of the treating physician or if they are being involuntarily admitted. Vital sign monitoring every 5 minutes will ensure adverse drug reactions are addressed promptly.

Although the dose used should not induce emergence reaction, it should be noted that transition to conscious perception can be terrifying, and severe emergence reaction can be a traumatic experience. This effect will be inherently mitigated through the low dosage used. Furthermore, pre-induction coaching, slow infusion, and PRN administration of midazolam strategy will be used to mitigate this potential adverse side effect.

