Suicidal patients, subjectively identified by clinician, upon admission to the ED will be medically cleared by the EM physician, and then meet with the mental health liaison to be screened for admission to the psychiatric department, per normal standard of care. Study investigators will not be available around the clock, but when available will begin the pre-screening method for this investigation. The treating physician will pre-screen them for inclusion and exclusion criteria per an IRB approved check list (Appendix D: Criteria Checklist).

The patient will be approached for informed consent in accordance to with 21 CFR 50. They will be provided with a written document that embodies the elements of the informed consent. The consent will be presented orally to the subject with a witness. Once presented the subject will be given a reasonable time to review the contents and inquire information. Upon signing of the form, a copy shall be given to them.

Once consent is obtained, they will be presented with a paper form to complete the BSSI and MADRS-S. These measures will serve as baseline severity of suicidal wishes and plans, and degree of depression symptoms. Questionnaires will be stored in locked drawer's in the locked office the Division Officers in the Emergency Department, the Inpatient Mental Health ward, or the study coordinator.

Once the patient is deemed medically cleared by the treating physician, the study treatment will be ordered by an ED provider, per the randomization schedule, and administered by an ED nurse (Please see below for more detailed methodology). Those in the experimental arm will be treated with 0.5 mg/kg IV infusion of ketamine over 40 minutes. Those in the control arm will be treated with 100 cc Saline infusion over 40 minutes. (Table 1) Since there are no pharmaceutical treatment specific for acute suicide, it is in accordance to the Declaration of Helsinki (DOH) to utilize a saline placebo control. Vitals will be checked every 5 minutes during infusion. Questionnaires will be repeated at four time points for both arms, once in the ED before drug administration, one at 4 (+/-1) hours post-infusion, whether in the ED or the psychiatric unit, another 24-36 hours after the infusion in the inpatient psychiatric unit, and lastly one-week (+1 day) post treatment by phone call.

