## Methods and Materials

All procedures in the management of the acutely suicidal patient will be in accordance with the standard of care, which includes a focused history and physical by an Emergency Medicine physician. Figure 1 demonstrates the flow of investigational procedures. The EM provider shall medically screen the patient and include appropriate ancillary studies. For example, if a patient is altered, intoxicated, sick-appearing, or exhibiting a clinical toxicodrome, standard labs, EKG, or imaging will be ordered per standard of care. All female patients will have a urine HCG documented. Then, screening for admission to the psychiatric department will be done by the mental health liaison. This standard procedure will serve secondarily as the pre-screening method for this investigation. This will minimize duplication of work.

Once the patient is deemed "to be admitted to the psychiatric unit," the physician will check the Electronic Medical Records (EMR) for inclusion and exclusion criteria. If a patient's current medication has a possible interaction with ketamine, the ordering provider will consider consulting with the inpatient pharmacist about possible contraindications, which will be documented in the chart. Once screened as a potential subject for the study, the patient will be approached for consent. Consent explaining the research protocols, benefits, and risks will be obtained once by a member of the investigative team. Consent will be obtained from a clinically sober intervention-eligible patient, who is accepted to inpatient psychiatry. It will be obtained while in the ED. Subjects will consent on an individual basis. Consent will be documented on a standardized consent form approved by the IRB. Any female patient will undergo a pregnancy test to verify eligibility.

Once the patient is enrolled, the physician will calculate the dosage based on actual weight and place the order in the electronic medical record. The emergency department nurse assigned to the care of the patient will fax the order to the pharmacy. At this point, the pharmacy will follow the randomization instruction and schedule, and undergo three safety checks per pharmacy protocol. (Appendix D: Randomization List & Instructions.) The medication will be treated as a controlled substance and will require a nurse or clinician to pick it up from the inpatient pharmacy.

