## 12.5 Inclusion Criteria:

| Order Number                             | Criteria   |
|--|--|
| Subject Inclusion and Selection Criteria |  |
| 1  | 
1. Patient demographics will consist of Active, Reserve, or retired military personnel or their dependents.
 Subjects must meet the following inclusion criteria:
 
2. Adult (18 to 89 years old)
 3. Present with active SI
 4. Deemed to be admitted to inpatient psychiatric unit
 |

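### Section 14.2 excludes past psychosis, schizoaffective disorder and involuntary admission, but the eligibility lists in 12.5 and 12.6 contain none of the three

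*Combined protocol and SAP*

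**What the plan says.** Section 14.2, under Minimization of Risks, names groups that will be kept out of the trial. On psychiatric history it says: "We will be excluding those patients most vulnerable to adverse events, such as those with a history of psychosis, schizophrenia, or schizoaffective disorder". It excludes pregnant patients, and then adds: "Patients will also be excluded medically at the discretion of the treating physician or if they are being involuntarily admitted".

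The formal criteria are in 12.5 (four items) and 12.6 (ten items). The two psychosis-related items in 12.6 are "Currently presenting with psychosis as determined by mental health consultant" and "Have a personal/family history of Schizophrenia". The only admission-related item in 12.5 is "Deemed to be admitted to inpatient psychiatric unit", with no condition on whether the admission is voluntary.

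Screening is described in three places:

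- 10.1, General Approach: "The treating physician will pre-screen them for inclusion and exclusion criteria per an IRB approved check list". The checklist is in Appendix D.
- 10.1, Methods and Materials: once admission is decided, "the physician will check the Electronic Medical Records (EMR) for inclusion and exclusion criteria".
- 13.1, Subject Recruiting Methods: the mental health liaison, with the on-call mental health provider, "determines whether or not patient requires inpatient psychiatric hospitalization".

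**The concern.** A protocol should have one set of eligibility rules. Here the section that justifies the risk to subjects relies on exclusions that the eligibility lists omit. A patient can meet every item of 12.5, trigger none of 12.6, and still belong to a group that 14.2 says is excluded.

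Two things are at stake.

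- **Safety.** Section 14.2 describes the psychosis-spectrum group as the one most vulnerable to adverse events. Section 14.1 lists psychosis-like effects among the risks of low-dose IV ketamine. If the lists used at the bedside omit part of that group, the stated safeguard does not work as described.
- **Interpretation.** Involuntary admission is a separate ground, and 14.2 does not attach the same vulnerability label to it. It still matters who is included. All subjects are being admitted to a psychiatric unit, and whether the trial covers only voluntary admissions changes the population to which the result applies.

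**Working it through.** There is no statistical figure to reproduce. The check compares each exclusion in 14.2 with the four items of 12.5 and the ten items of 12.6.

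| Exclusion stated in 14.2 | Counterpart in 12.5 or 12.6 | Result |
|---|---|---|
| Past psychosis | 12.6 item 2 covers current psychosis only | Absent |
| Schizophrenia | 12.6 item 4 (personal or family history) | Present |
| Schizoaffective disorder | Not named; item 4 names schizophrenia only | Absent |
| Pregnancy | 12.6 item 5 | Present |
| Medical exclusion by the treating physician | Nearest are 12.6 items 6 and 7 (unstable illness, no medical clearance) | Broadly present |
| Involuntary admission | No condition on legal status in either list | Absent |

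Count: 6 stated, 3 with a counterpart, 6 − 3 = 3 without.

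Could an existing item be read to cover the three?

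- *Past psychosis.* Item 2 is limited to the current presentation. Item 4 catches past psychosis only where the diagnosis was schizophrenia or there is a family history of it. Remitted psychosis from another cause passes.
- *Schizoaffective disorder.* Section 14.2 names it separately from schizophrenia, so the protocol does not itself treat one term as covering the other. A patient with this diagnosis, no current psychosis and no schizophrenia history passes.
- *Involuntary admission.* The admission item in 12.5 is met by either legal status.

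Do the screening steps close the gap?

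- The record check in Methods and Materials looks for the inclusion and exclusion criteria. It adds none.
- The liaison interview in 13.1 decides whether admission is needed. It is not described as establishing legal status or past psychosis.
- Section 13.4 bars decisionally impaired patients and defers intoxicated ones. That is a different group: a patient with remitted psychosis, or one admitted involuntarily, may have capacity.
- The Appendix D checklist is not in the supplied text and cannot be checked.

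A patient wrongly enrolled would be randomised to arms of 31 and 31 under 11.4, so about half (31/62) of such patients would receive ketamine.

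There is also a smaller difference in the other direction. Section 12.6 excludes a family history of schizophrenia, and 14.2 does not mention it.

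**The case against.** The strongest reply is that this is an omission and not a contradiction. Neither 12.5 nor 12.6 says that these patients may enter, and 14.2 belongs to the same protocol and says they will not. Read as a whole, the protocol excludes them. Pre-screening uses the Appendix D checklist, which may carry all three items, and the recruitment flow is in Figure 1, which is not reproduced. The route to harm therefore runs through material that is not available here.

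Other safeguards also reduce the risk. Every candidate sees the mental health liaison, and a mental health consultant judges current psychosis. Section 14.2 leaves room for physician discretion. The research monitor section provides for a capacity assessment at consent, and the monitor can remove subjects. Section 10.1 requires vital signs every 5 minutes, an attendant throughout, and stopping rules. Finally, 14.2 introduces its psychiatric diagnoses as examples, so the count of six depends on how the paragraph is read.

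Much of this stands as a limit on the consequence. The mismatch between sections is certain; wrong enrolment is only possible. The safeguards narrow the residual group to remitted psychosis outside schizophrenia, schizoaffective disorder without current psychosis, and involuntary status. No effect on the randomised comparison, the significance level or power is claimed.

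None of it removes the inconsistency. Silence in the eligibility list is the defect, because a patient who passes every listed item appears eligible. Presenting the diagnoses as examples allows more groups to be added but does not make the named ones optional. Discretion is stated alongside the three rules and not in their place. Monitoring during infusion acts only after the patient has been enrolled. If the checklist does contain the three items, it agrees with 14.2 but differs from 12.5 and 12.6, and the texts still need reconciling.

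**Conclusion.** The concern holds. On a direct reading, three of the six exclusions in 14.2 (past psychosis, schizoaffective disorder, involuntary admission) are missing from 12.5 and 12.6, and no other supplied section adds them. The text is wrong as written, and it should be corrected before enrolment because following the formal criteria exactly could defeat a stated safety measure.

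The consequence for patients is conditional on staff screening from 12.5 and 12.6, or from a checklist that mirrors them. Its size is unknown: the documents give no frequency for any of the three conditions, so no number out of 62 can be given.

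**What to change.** Before enrolment, reconcile 12.5, 12.6, 14.2 and the Appendix D checklist so that all four give the same criteria. Past psychosis, schizoaffective disorder and current involuntary admission should each appear in every place or in none. Settle the family history of schizophrenia item in the same pass. If Figure 1 shows eligibility steps, bring it into line too. Which version of each rule is right is a decision for the investigators and the review board.

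The cost is a text amendment to the criteria tables or to 14.2, plus the checklist if it differs. Psychiatric history is already collected by chart review under 10.2, so checking the two diagnostic items would need little new work. If the 14.2 exclusions are kept, the eligible pool shrinks by an amount that the documents do not allow to be estimated.
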